# 4.2 Exclusion Criteria

1) Patients currently receiving therapy for mucositis.

# 5.0 Treatment Plan

There will be a total of 180 patients in this study. There will be a cohort of 100 patients on mTOR-based regimens (Phase I or Phase II) which will be enrolled in the Department of Investigational Cancer Therapeutics. There will be a cohort of 80 patients on radiation regimen which will be enrolled in the Department of Radiation Oncology.

# 5.1 Drug Administration and Treatment Schedule

This is randomized, double blinded, placebo-controlled trial examining Glutamine in patients receiving therapy with either mTOR inhibitor based therapy or radiation to the esophagus. Patients will be randomly assigned to receive Glutamine or Placebo. The study will be conducted in the Department of Investigational Cancer Therapeutics and the Department of Radiation Oncology at The University of Texas MD Anderson Cancer Center in Houston, Texas.

Patients will take 1 scoop (4 grams) of glutamine or placebo mixed with water twice each day.

Caution: New Drug-Limited by Federal Law to Investigational Use.

Patients will be randomized to glutamine or placebo by the MDACC Investigational Pharmacy (Section 12.5). Patients will be dispensed the study drug (glutamine or placebo) in a plastic bottle. Each bottle will contain 30 doses (scoops), which will be enough study drug for 15 days. A monthly supply (2 bottles) will be dispensed to patients.

Per MDACC policy, any unused or expired drug will be disposed of by the Investigational Pharmacy.

# 5.1.1 mTOR Inhibitor Therapy

Four weeks of treatment constitute 1 cycle for patients on mTOR inhibitor therapy. Glutamine will start on day 1 of mTOR inhibitor treatment. Patients may be allowed to continue the treatment if there is clinical response (to include prevention or resolution) of any mucositis. Patients will be treated on the double, blinded placebocontrolled trial for as long as they are on mTOR inhibitor therapy. If the patient stops the mTOR inhibitor based therapy, mucositis treatment should continue for 4 weeks after the last dose of mTOR-inhibitor-based regimen to prevent further mucositis complications.

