# 2.0 Background

# 2.1 Introduction

# 2.1.1 mTOR Inhibitors and Mucositis

Temsirolimus (Torisel; Wyeth Pharmaceuticals, PA) is a mammalian target of rapamycin (mTOR) inhibitor that gained FDA approval in 2007 for the treatment of advanced renal cell carcinoma. Another mTOR inhibitor, everolimus, has been approved for renal cell carcinoma, breast cancer, and neuroendocrine tumors. In addition, mTOR inhibitors have demonstrated encouraging efficacy results in patients with a range of advanced malignancies, alone or in combination with other chemotherapy agents or targeted therapies in trials for multiple forms of malignancies. As a central regulator of key pathways important in the proliferation of cancers, the mTOR inhibitor blocks the aberrant activation of phosphoinositide 3-kinase (PI3K)/Akt signaling pathway, resulting in growth arrest of cancer cells halting in the G1 phase of the cell cycle.

In general, mucositis is among the most common side effects reported from mTOR inhibitor-based treatment, which seems to be dose-related and occurs mostly in earlier cycles. It has been identified repeatedly as one of the most common dose-limiting toxicities. The mucositis incidence related to temsirolimus treatment as a single

agent was 41% in patients with solid tumors with 3% of grade 3 or above. However, 2 recent reviews of temsirolimus-based treatment demonstrated that the mucositis incidence rate ranged from 60-65% with 5-10% of patients developing Grade 3. The treatment that Investigational Cancer Therapeutics generally uses for the management of mucositis uses the following: xyloxylin (1:1:1 ratio of diphenhydramine, Maalox, lidocaine; 10 milliliters (mL) swish/ swallow every 6 hours as needed). This treatment is not used prophylactically, but used when patient develops mucositis. There is no standard mucositis treatment; therefore, it is important to improve mucositis treatment for patients on therapy with mTOR inhibitors.

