# 12.2 Study Endpoints

# **Primary Endpoints**

• For mTOR inhibitor patients, the severity of oral mucositis will be taken as the maximum grade observed during the 6-month study period. For esophagus radiation patients, the severity of esophagitis will be taken as the highest grade observed by week six.

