### 12.4 Statistical Analysis Plan

Note: Analyses will be performed separately for patients treated with mTOR inhibitors and patients with esophagus radiation.

For the primary objective, we will use the Wilcoxon rank sum test to compare the ordered categories of mucositis/esophagitis severity between treatment arms. A patient must complete at least 60% of the planned doses of placebo or glutamine to be considered evaluable in the statistical analysis. As a sensitivity analysis for the appropriateness of 60% dosing cut-off, we will analyze the outcome according to the proportion of drug taken. The proportional of drug taken will be computed as the ratio of number of doses taken to the total number of doses prescribed. For the mTOR inhibitor group, the denominator will reflect the total time that each patient is on the study. For the esophagus radiation group, the denominator will reflect the total number of doses that are prescribed during the delivery of radiation.

For the secondary objectives/endpoints, we will compare between treatment arms (1) the trajectories of the mucositis/esophagitis scores over time using linear mixed effects; (2) the proportion of patients developing mucositis/esophagitis using a Pearson chi-squared test; (3) the proportion of patients developing grade 3 or higher mucositis/esophagitis using a Pearson chi-squared test; (4) the duration of mucositis/esophagitis using the Wilcoxon rank sum test; (5) the time to develop mucositis/esophagitis using Kaplan-Meier estimates and the log rank test (due to right censoring in patients not developing mucositis/esophagitis); (6) the proportion of patients having treatment interruptions using a Pearson chi-squared test; (7) the

weight change using the Wilcoxon rank sum test; and (8) the QOL survey scores using the Wilcoxon rank sum test.

For the secondary objective of describing the toxicity profile, descriptive statistics will be provided on the grade and type of toxicity by treatment arm.

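### The 60%-of-doses rule in section 12.4 can remove mTOR patients from the primary comparison for reasons linked to the outcome, and no all-randomized analysis is named; section 5.1.1 is one possible route

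*Combined protocol and SAP*

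**What the plan says.** **Who is analyzed.** Section 12.4: "A patient must complete at least 60% of the planned doses of placebo or glutamine to be considered evaluable in the statistical analysis". The proportion is defined as "the ratio of number of doses taken to the total number of doses prescribed", and then: "For the mTOR inhibitor group, the denominator will reflect the total time that each patient is on the study". The only sensitivity analysis offered is that "we will analyze the outcome according to the proportion of drug taken". No analysis of all randomized patients appears.

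**What is measured.** In section 12.2, for mTOR patients, "the severity of oral mucositis will be taken as the maximum grade observed during the 6-month study period".

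**When study drug continues.** Section 5.1.1 has two adjacent sentences: "Patients may be allowed to continue the treatment if there is clinical response (to include prevention or resolution) of any mucositis", followed by "Patients will be treated on the double, blinded placebocontrolled trial for as long as they are on mTOR inhibitor therapy". It then extends dosing to four weeks after the last mTOR dose.

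**Removal, supportive care and end of study.** Grade 4 is the only mucositis-based removal reason in section 8; refusal of study medication is also listed. Section 9 and Appendix A let the physician add supportive therapy for persistent grade 1 or for grade 2 and above. Section 8 (item 3) and section 5.3.4 date completion and end of study from the last mTOR dose, or from six completed cycles. Neither dates them from an early stop of study drug.

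**Timing.** Section 2.1.1 says of mTOR mucositis that it is an effect "which seems to be dose-related and occurs mostly in earlier cycles".

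**The concern.** The primary population is defined by something that happens after randomization. If taking fewer doses is a consequence of mucositis, patients are selected for analysis on the outcome being compared. Because the endpoint is a maximum grade, the grade that prompts a stop has already been observed, so the 60% rule would discard a known result.

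Section 5.1.1 offers a concrete path. A permission to continue given response can be taken to mean that it may be withheld without response. Four things must then all hold:

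1. a physician uses that sentence to stop study drug while mTOR therapy continues;
2. the patient remains on study;
3. the denominator keeps accruing over total time on study;
4. the stop comes before 60% of that time.

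The stake is a primary comparison that loses some of its most informative patients, mainly from the arm with more mucositis.

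**Working it through.** **Inputs.** From section 12.3: control grades 0-1/2/3 of 69/22/9%, glutamine 95/5/0%, 50 per arm, two-sided 5% Wilcoxon test, stated power 94%. Cycles are 28 days (section 5.1.1). Six cycles are taken as the 6-month period. Loss rates are assumptions, because the documents give none.

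**1. The plan's power.** P(control grade higher) + ½P(tie) = 0.69×½×0.95 + 0.22×(0.95 + ½×0.05) + 0.09×1 = 0.632. Pooled proportions are 0.82, 0.135 and 0.045; the sum of their cubes is 0.554. Tie-corrected formula: Φ(√(3×100/(1−0.554))×0.132 − 1.96) = 92.9%. Simulation of the tie-corrected test (200,000 runs) gives 96.1%. The stated 94% lies between the two. Later figures use simulation, so compare them with 96.1%.

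**2. When a stop breaches 60%.** Assume full adherence up to the stop and a denominator that runs over all time on study.

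- Six cycles: 0.60×168 = 100.8, so about day 101.
- Six cycles plus the four post-mTOR weeks: 0.60×196 = 117.6, so about day 118.

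| Stop at end of cycle | Share of 168 days | Share of 196 days |
|---|---|---|
| 1 | 28/168 = 17% | 28/196 = 14% |
| 2 | 56/168 = 33% | 56/196 = 29% |
| 3 | 84/168 = 50% | 84/196 = 43% |
| 4 | 112/168 = 67% | 112/196 = 57% |

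Stops in cycles 1 to 3 fail on either count; a stop after cycle 4 passes on one and fails on the other. A shorter mTOR course moves the threshold earlier (week 7.2 of 12, for example). If the denominator ends when drug is stopped, or the patient leaves the study then, the ratio is 100% and the patient stays in.

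**3. Equal loss in both arms.** If a share l of grade 2+ patients is lost, the observed grade 2+ proportion is p(1−l)/(1−pl), with p = 0.31 (control) or 0.05 (glutamine).

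| l | Control | Glutamine | Difference (points) | Simulated power |
|---|---|---|---|---|
| 0% | 31.0% | 5.0% | 26.0 | 96.1% |
| 10% | 28.8% | 4.5% | 24.3 | 94.3% |
| 25% | 25.2% | 3.8% | 21.4 | 90.4% |
| 50% | 18.3% | 2.6% | 15.8 | 76.3% |

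Grade 2+ only approximates those at risk: patients who resolve would continue, while unresolved grade 1 could also be stopped.

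**4. Type I error** (69/22/9% in both arms). Equal loss of 0, 10, 25 or 50% gives 4.9 to 5.0%. Unequal loss gives 5.6% (10% vs 0%), 5.7% (20% vs 10%) and 9.5% (25% vs 0%).

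**5. Price of including everyone.** Worst case: a share d of the glutamine arm has low exposure and gets no benefit, so follows the control distribution. At d = 10% the glutamine arm is 92.4/6.7/0.9% and power is 88.4%. At d = 20% it is 89.8/8.4/1.8% and power is 76.2%. Dropping 10% or 20% of each arm at random, with full effect in the rest, gives 94.1% (45 per arm) or 91.2% (40 per arm).

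**The case against.** **The plan does not tell anyone to stop.** A reader might infer that section 5.1.1 makes unresolved mucositis a stopping rule. The documents do not support that. The sentence is permissive, the one after it sets duration without any mucositis condition, section 8 removes patients for mucositis only at grade 4, and section 9 responds to lower grades with added supportive therapy. This objection stands. What remains is a loosely drafted sentence that a physician could use, with nothing expressly withdrawing its condition.

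**A stopped patient may still be evaluable.** Section 12.4 also speaks of doses prescribed, and doses a physician has stopped are arguably no longer prescribed. A patient refusing study drug can be removed under section 8. On either reading the ratio is not reduced. Against this, the mTOR denominator is tied to total time on study, whose end is dated from mTOR therapy. The text points both ways.

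**The harm may be small.** At 10% loss power is still about 94%. That equals the stated figure only because the simulation starts at 96%; the like-for-like fall is about two points. No passage supports a loss as high as 50%.

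**False positives.** A reader might infer that the rule inflates type I error. With no effect on grade, blinded stopping driven by grade acts alike in both arms, and the rate stays near 5%. Inflation needs unequal loss between arms, for which some other cause must be supposed; section 12.5 describes a placebo matched in appearance and taste.

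**The main remedy does not depend on 5.1.1.** True: the all-randomized analysis answers a general weakness of the 60% rule. That is why the rule is the point here and 5.1.1 only one route to it.

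**Conclusion.** The concern holds in a limited form. Section 12.4 conditions the primary mTOR test on post-randomization dosing that can depend on the outcome, and names no all-randomized analysis as a safeguard. The analysis by proportion of drug taken may reveal a pattern but leaves the primary test unchanged.

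Exclusion through 5.1.1 is possible, not automatic: it needs all four conditions, and the documents give no rate for any of them. If they hold, early onset makes a stop before the threshold plausible. The likelier consequence under blinding is attenuation with some lost power, sized by the assumed loss rates above. Severity is minor to moderate, with medium confidence. The case for acting rests on the low cost of the change, not on evidence that the problem will be frequent.

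**What to change.** **Section 12.4.** Replace the evaluability rule for the mTOR cohort with text such as:

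> The primary Wilcoxon comparison in the mTOR cohort includes all randomized patients, each with the highest mucositis grade observed in the 6-month period, whatever proportion of doses was taken. Patients with no post-baseline grade, and patients whose observation ended early, are reported by arm. The comparison limited to patients with at least 60% of planned doses is a sensitivity analysis.

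Reporting truncated observation matters because a patient who withdraws after one early grade 0 would otherwise enter as grade 0-1 without comment.

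**Section 5.1.1.** Delete the response sentence, so that study drug runs throughout mTOR therapy subject only to section 8, in agreement with the sentence that follows it.

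**Cost.** The change is two text edits. It adds no visits or data, since grading already follows the mTOR cycles (section 5.3.3). Inclusion would no longer depend on how the denominator is read or why drug was stopped. The downside is the dilution in step 5: worst-case power of about 88% or 76% with 10% or 20% no-benefit patients in the glutamine arm. The retained 60% analysis shows the result without low-exposure patients.

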# 5.1.2 Radiation to the Esophagus

Radiation must be  $\geq$ 45 Gy delivered alone or with concurrent chemotherapy. The type of concurrent chemo will be determined by the treating physician. For the esophagitis arm, induction chemotherapy is allowed. XRT must be given using

conventional daily fraction dose from 180-240 cGy per day. Radiation technique may include: 3D conformal, IMRT, and or protons. Glutamine will start on the first day of radiation, or within 10 days of the start of radiation and will be continued for 4 weeks after the last day of radiation. Radiation will be given daily (Monday through Friday) for 5 days per week. The number of weeks of radiation therapy will be determined by the treating physician. The end of treatment week will vary based on the number of weeks of radiation that the patient receives.

[figure not shown]

Figure 3. Treatment Regimen (Schema)

For patients who will receive mTOR inhibitor based therapy: the patients will be randomized to receive either placebo or Glutamine beginning on Day 1 of an mTOR inhibitor based therapy.

**For patients who will receive radiation to the esophagus:** the patients will be randomized to receive either placebo or Glutamine beginning on Day 1 of radiation treatment, or within 10 days of the start of radiation.

# 5.2 Evaluation of Response

For patients receiving mTOR inhibitor-based therapy, the patients will be evaluated weekly during the first 4 weeks of treatment for signs and symptoms of mucositis in the clinic using the CTCAE version 4.03 (Section 9.0). After four weeks of therapy, mucositis symptoms may be assessed by in person interview or phone call to the patient. If mucositis symptoms are  $\geq$  grade 2, the patient will be asked to visit clinic for oral examination.

For patients receiving radiation therapy, the patients will be evaluated weekly based on the number of weeks of radiation therapy as determined by the treating physician, at end of treatment (or final week of radiation treatment based on number of weeks of radiation), 1 month, and 6 month post radiation therapy for signs and symptoms of esophagitis using the CTCAE version 4.03 (Section 9.0). Esophagitis symptoms may be assessed by in person interview or phone call to the patient.

### 5.3 Study Assessments and Procedures

Evaluation will take place as per protocol schedule unless patient/logistical/medical reasons intervene.

### 5.3.1 Assessment of Improvement in Quality of Life

### MD Anderson Symptom Inventory (MDASI-HN)

MDASI was designed to assist in the assessment of 13 symptoms common in cancer patients (dry mouth, fatigue, pain, disturbed sleep, drowsiness, feeling of being distressed, anorexia, sadness, numbness/tingling, dyspnea, difficulty remembering, nausea, and vomiting) during the previous 24 hours. In addition, 9 head and neck cancer specific items are included in MDASI-HN which are mouth sores, taste, constipation, teeth/gum problems, skin pain, difficulty with voice, choking/coughing, difficulty swallowing, and problem with mucus. The severity at the time of assessment of each symptom is rated from 0 to 10 on a numerical scale, 0 meaning that symptom is absent and 10 meaning that it is of the worst possible severity. The instruments and techniques are both valid and reliable in the assessment of the intensity of symptoms in cancer populations.

For patients receiving mTOR inhibitor-based therapy, the MDASI-HN will be administered at baseline, Day 15, Day 1 of Cycle 2 and beyond, end of study visit and 3 months (+/-14 days) and 6 months (+/-21 days) post end of mTOR inhibitor-based therapy. These questionnaires may be administered over the phone.

For patient receiving radiation, the MDASI-HN will be given at baseline, Week 3, Week 5, Week 7, end of treatment (or final week of radiation treatment based on number of weeks of radiation), at 1 month (+/-7 days), 3 months (+/-14 days), and 6 months (+/-21days) after radiation. These questionnaires may be administered over the phone.

### Measure of Patient Satisfaction with Study Medication Satisfaction Scale

The Study Medication Satisfaction Scale is a short, 7-item scale, that asks patients about several areas of satisfaction. The scale includes questions about ease or difficulty of taking the medication in general and in its current form, convenience of taking the study medications as instructed and patient confidence that the study medication is of benefit.

For the patients receiving mTOR inhibitor-based therapy, the patient satisfaction scale will be given on Day 1 of Cycle 2 and beyond.

For the patients receiving radiation, the patient satisfaction scale will be given at Week 3, Week 5, Week 7, end of treatment (or final week of radiation treatment based on number of weeks of radiation), and 1 month post radiation therapy.

These surveys may be administered over the phone.

# 5.3.2 Pretreatment Evaluations:

To be completed within 4 weeks prior to initiation of therapy:

- Medical history including list of current concomitant medications and history of mucositis and esophagitis with prior therapy (mucositis and esophagitis history may be obtained by retrospective medical record review).
- Examination of oral mucosa.
- Informed consent
- Weight
- ALC (absolute lymphocyte count)
- Quality of life Questionnaire: MDASI-HN for all patients.
- Medical photograph of oral mucosa for patients receiving therapy with an mTOR inhibitor containing regimen. Attempts to perform medical photographs will be made at this timepoint, but if unsuccessful, will not be considered a deviation to the protocol since it is not a safety assessment.
- Women of childbearing potential will have a pregnancy test using urine and/or blood, and periodically as clinically indicated

# 5.3.3 Evaluation during Study:

- Examination of oral mucosa and grading of oral mucositis weekly during cycle 1 and monthly in subsequent cycles for patients receiving mTOR inhibitor therapy. For patients receiving radiation to the esophagus signs and symptoms of esophagitis (ie: dysphagia, weight loss) are to be evaluated in the routine monitoring weekly visits during therapy, as per the study calendar below.
- Weights to be obtained weekly during cycle 1 and monthly in subsequent cycles for patients receiving mTOR inhibitor therapy. For patients receiving radiation to the esophagus weights are to be obtained weekly during XRT.
- Concomitant medications to be reviewed weekly during cycle 1 and monthly in subsequent cycles for patients receiving mTOR inhibitor therapy and weekly, 4

weeks post last radiation and at 6 months post last radiation for patients receiving radiation to the esophagus .

- Quality of life questionnaire. MDASI-HN for patients receiving mTOR inhibitor therapy on day 15 and day 1 of Cycle 2 and beyond, end of study visit, and 3 months (+/-14 days) and 6 months (+/-21 days) post end of mTOR inhibitor-based therapy. Patients receiving radiation to the esophagus should complete the questionnaires at the Week 3, Week 5 and Week 7, end of treatment (or final week of radiation treatment based on number of weeks of radiation), as well as 1 month (+/-7 days) and 3 months (+/-14 days), and 6 months (+/-21 days) after treatment.
- Patient Satisfaction Survey will be given on Day 1 of Cycle 2 and beyond for patients receiving mTOR inhibitor therapy and given at Week 3,Week 5, Week 7, end of treatment (or final week of radiation treatment based on number of weeks of radiation), and 1 month post treatment for patients receiving radiation to the esophagus.
- For patients on mTOR inhibitor-based therapy, ALC may be obtained at screening and Day 1 of Cycles 2 and beyond. Attempts to perform ALC labs will be made at this timepoint, but if unsuccessful, will not be considered a deviation to the protocol since it is not a safety assessment.
- For patients on radiation therapy, ALC may be weekly during radiation. Attempts to perform ALC labs will be made at these timepoints, but if unsuccessful, will not be considered deviations to the protocol since these are not safety assessments.
- Medical Photograph of oral mucosa at the worst grade of mucositis and at cycle 1 day 29 (prior to cycle 2) for patients receiving therapy with an mTOR inhibitor containing regimen. Attempts to obtain medical photographs will be made at this timepoint, but if unsuccessful, will not be considered a deviation to the protocol since it is not a safety assessment.

